**Table 4 Schedule of Events for IM Group (HIV-Infected and HIV-Uninfected Subjects)**

Day	Screen*	1	BL	3	8	11	15	17	22	25	29	43	57	59	64	67	71	73	78	81	85	113	99 	F/U 	
	Week	NA	0	1	1	2	2	3	3	3	4	6	8	8	9	9	10	10	11	11	12	14	16		
Visit window (days)	(-28 days)	NA	±3	hr	±1	±1	±1	hr	±1	±1	±1	±1	±1	hr	±1	hr	±1	±1	±1	±1	hr	±1	±1		
ACTIVITIES TO BE COMPLETED BEFORE STUDY DRUG ADMINISTRATION																									
Review/discuss Inclusion/Exclusion criteria	X																								
Obtain signed Informed Consent Form	X																								
Record demographics, medical history (general and HIV); height	X																								
Record agents in ART history at Screening, changes in ART on-study 	X	X				X			X	X	X						X				X 				
Record results of a complete physical examination	X																								
Record results of a targeted physical examination 		X			X			X	X	X						X				X	X 				
Record vital sign measurements	X	X			X			X	X	X						X			X	X 					
Record the patient's weight	X																			X 	X 				
Record AEs 	X	X			X			X	X	X						X				X	X	X	X	X	
Assess injection site									X	X	X	X	X	X	X	X	X	X	X	X	X	X	X		
Record concomitant medications	X	X			X			X	X	X						X				X					
HIV Treatment Satisfaction Questionnaire (HIVTSQs)									X 											X 					
HIV Treatment Satisfaction Questionnaire (HIVTSQc)																				X 					
Study Medication Satisfaction Questionnaire (SMSQs)									X 										X 						
Study Medication Satisfaction Questionnaire (SMSQc)																			X 						
BLOOD and/or URINE SAMPLES TO BE COLLECTED																									
Hematology and serum chemistry (see Section 7.2.1 for list)	X	X			X			X	X	X						X				X	X 				
Urinalysis	X	X			X			X	X	X						X				X	X 				
HIV-1 RNA (viral load) 	X	X			X			X	X	X						X				X					
4 th Generation POC HIV test 		X						X	X	X						X					X				
CD4+ cell count	X	X						X	X	X										X 	X 				
Serum for pregnancy test for females of childbearing potential 	X																		X 	X 					
Urine for pregnancy test for females of childbearing potential		X			X 			X	X 	X						X 									
Antiretroviral resistance sample 	X			X			X	X	X							X				X					
Archive serum sample		X			X			X	X	X						X				X	X 				
Trogarzo® serum concentration (pre-dose if drug administered on this day) 		X	X	X	X	X	X	X	X	X	X	X	X	X	X	X	X	X	X	X	X	X 			

Day	Screen*	1	BL	3	8	11	15	17	22	25	29	43	57	59	64	67	71	73	78	81	85 	99 	113 
		0	1	1	2	2	3	3	3	4	6	8	8	9	9	9	10	10	11	11	12	14	16
Week	NA	±3				±3						±3		±1	±1		±3		±1	±1	±1	±1	±1
Visit window (days)	(-28 days)	NA	hr	±1	±1	±1	hr	±1	±1	±1	±1	±1	hr	±1	±1	±1	hr	±1	±1	±1	±1	±1	±1
Immunogenicity of Trogarzo® (2 tubes x 3 mL each)		X																		X 	X 		

#### STUDY DRUG ADMINISTRATION AND AFTER

Administer study drug via IVI – study drug diluted in 250 mL normal saline and administered IV over 15 minutes per Trogarzo® prescribing information

Administer study drug via IM injection

Observe subject for 15 minutes if HIV infected and 60 minutes if HIV uninfected after administration; record vital sign measurements after dose administration and again at end of observation period

\* Screening visit to be conducted for HIV-infected patients ONLY. See [Table 2](#) for Screening and Pre-Steady State Phase Schedule of Events

 All prior ART will be recorded at Screening; subsequent visits will only record changes to ART.

 Abbreviated physical examination includes examination of lymph nodes, respiratory and cardiovascular systems, abdomen, extremities, and nervous system.

 Only record AEs that are related to study procedures before administration of the first dose; after administration of first dose, assessments will include evaluation of injection site for reaction.

 Subjects need not fast before blood sampling.

 Serum FSH test to be conducted on postmenopausal females at Screening only.

 Pre-dose samples to be collected within 1 hour before the start of the infusion.

 At Baseline and at Day 15, subjects in the IM Group will receive study drug diluted into 250 mL normal saline as an 800 mg IV infusion over 15 minutes, per Trogarzo® prescribing information. At Day 29 IM Group subjects will begin receiving study drug as 800 mg undiluted Trogarzo® administered by IM injection once every 2 weeks.

 Any abnormalities observed need to be recorded on the AE case report form.

 HIV-infected IM group subjects only.

 HIV-uninfected IM subjects only.

 Day 85 is end of study for HIV-infected subjects.

 Day 99 is follow-up for HIV-infected subjects and is end of study for HIV-uninfected subjects.

 PK visits between Baseline and Day 29 will not be required for HIV-infected subjects participating in the IM portion of TMB-302 who have re-enrolled after receiving a 2000mg loading dose and one 800 mg dose of Trogarzo® by IVI prior to study re-enrollment since these PK samples will already have been collected during initial study participation.

## 3.5 Safety Assessments

Safety assessments will include the results of the following measurements through Day 99 (14 weeks) for the Sentinel Group and the HIV-uninfected Core and IM Groups Subjects, whose participation is 2 weeks longer in duration, Day 85 (12 weeks) for the HIV-1 infected Core and IM Group subjects:

- Physical examinations;
- Vital sign measurements;
- Clinical laboratory parameters (hematology, CD4+ T-cell counts, serum chemistry, and urinalysis);
- Monitoring of Aes and concomitant medications;
- Anti-Trogarzo® antibody levels (immunogenicity of Trogarzo®).
- Injection site reactions in subjects receiving Trogarzo® IM

## 3.6 Pharmacokinetic Assessments

Pharmacokinetic samples will be collected in the study to evaluate serum concentrations of Trogarzo®. These data will be used to allow evaluation of the PK profile of Trogarzo®. In particular, data will be collected to compare serum drug concentrations (AUC and trough) after IVI of the 800 mg diluted drug over 15 minutes to IV push of the undiluted drug over 30 seconds and IM injection. Study TMB-121 results showed that following 800 mg Trogarzo® via IM injection, the Tmax was 2.13 days. Therefore, for better estimation of AUC following IM injection, the timepoints of 2, 7, 10, and 14 days following dosing were selected. For comparison between IV infusion of the 800 mg diluted drug over 15 minutes and IM, blood will be collected at the same timepoints for both routes. See [Table 1](#), [Table 2](#), [Table 3](#), and [Table 4](#) for PK sample collection timepoints. HIV-1 infected participants who re-enroll after receiving a loading dose of 2000mg IVI and at least one maintenance dose of 800mg IVI given according to the label a minimum of 4 weeks prior to Day 1 enrollment will not undergo PK assessments between the Baseline and Day 29 visits since these PK samples will already have been collected during the subject's initial study participation. The PK assessments of the re-enrolled participants will be compared between the IVI from their first enrollment and IM from their second enrollment.

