## 1.3 Pharmacokinetic and Pharmacodynamic Profile

Intravenous administration of escalating single doses of Trogarzo® (Study Hu5A8.01) demonstrated that serum concentrations of Trogarzo® generally peaked at the end of the infusion period.

Trogarzo® pharmacokinetics were dose-dependent, as both systemic exposure and elimination half-life increased disproportionately with increasing dose. This indicated that the elimination of Trogarzo® is capacity limited and saturable at higher doses. A similar conclusion was reached after a multiple-dose study of IV Trogarzo® (Study TNX-355.02), which demonstrated that the steady-state half-life following multiple doses of 10 and 25 mg/kg was 75 and 79 hours, respectively. The capacity-limited elimination is likely due to CD4 receptor turnover, given the short half-life for Trogarzo® relative to endogenous immunoglobulin 4 (IgG4) molecules. In the IV Trogarzo® studies conducted to date, there was a correlation between Trogarzo® trough serum concentrations of 0.3 µg/mL or higher and saturated binding of CD4 (receptor occupancy) on CD4+ T-cells, and between CD4 receptor occupancy and reductions in HIV viral load.

The Phase 2b trial (Study TMB-202) investigated the correlation between Trogarzo® serum concentration, using an assay with 100 ng/mL sensitivity, and CD4 receptor occupancy. Paired measurements for individual subject samples were evaluated. Data were available for pre-dose samples collected at Baseline through Week 24, along with Baseline post-dose samples. The data evaluated were confined to those samples for which both serum Trogarzo® and receptor occupancy measurements were reported. Pharmacokinetic data were censored (as described in the clinical study report [CSR] Appendix 16.5) and receptor occupancy data were censored accordingly (mainly to eliminate outliers resulting from improper sample collection and/or labeling).

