## 6.1 Sentinel Group

Study drug administration visits will take place once every 2 weeks beginning at Day 1/Baseline and continuing through Day 99 (14 weeks). After the study drug administration at Day 85 (12 weeks) by IV push, Sentinel Group subjects will revert to routine administration of Trogarzo® diluted in 250 mL normal saline via IVI over 15 minutes in accordance with Trogarzo® prescribing information. The scheduled visit at Day 113 (16 weeks) is for safety follow-up only, and this visit may be conducted by telephone if no clinic visit is needed for this purpose. Trogarzo® administration at Day 113/follow-up should be conducted in the routine manner as employed prior to the study, through the primary care provider.

Safety assessments, including collection of blood and urine specimens for safety laboratory testing, as well as HIV-1 viral load and archive and viral resistance samples, will be conducted every 2 weeks beginning at Day 1/Baseline and continuing through Day 99 (14 weeks). Additionally, beginning at Day 29 (4 weeks), Sentinel Group subjects will also have non-laboratory safety assessments (vital signs, AEs, recording of concomitant medications) during visits on intervening weeks between the study drug administrations that are less than 15 minutes in duration (e.g., at Day 36 [5 weeks], Day 50 [7 weeks], Day 64 [9 weeks], etc.), through Day 92 (13 weeks).

Pharmacokinetic samples will be collected after the study drug doses at Day 1/Baseline, Day 15 (2 weeks), Day 71 (10 weeks), and Day 85 (12 weeks) at the following timepoints: 1 hour, 24 hours, 72 hours, 7 days, and 14 days after study drug administration. This schedule will require additional visits solely for sample collection on Study Days 2, 4, 8, 16, 18, 22, 72, 74, 86, 88, and 92.

Pharmacokinetic samples will also be collected on Days 1, 15, 29, 43, 57, 71, 78, 85, and 99 when visits are otherwise scheduled, and extra visits are not needed on these days for collection of these samples. The 1-hour, 24-hour, and 14-day post-dose serum concentration data are required for estimation of the PK AUC.

Study participants who

1. miss 2 consecutive visits or
2. have more than one treatment visit out of window or
3. have 3 non-treatment visits over 4 weeks that are out of window

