Safety assessments, including collection of blood and urine specimens for safety laboratory testing, as well as HIV-1 viral load and archive and viral resistance samples (HIV-infected subjects only), will be conducted every 2 weeks beginning at Day 1/Baseline and continuing through Day 85 (12 weeks) for HIV-infected subjects, and through Day 99 for HIV-uninfected healthy volunteers. In addition, beginning at Day 29 (4 weeks), Core Group subjects will also have non-laboratory safety assessments (vital signs, AEs, recording of concomitant medications) conducted during visits on intervening weeks between the IV push study drug administrations (e.g., at Days 36 [5 weeks], 50 [7 weeks], 64 [9 weeks], etc.), through Day 78 (11 weeks) for HIV-infected subjects, and through Day 85 (12 weeks) for HIV-uninfected healthy volunteers.

Pharmacokinetic samples will be collected after study drug doses at Day1/Baseline, Day 15 (2 weeks), Day 43 (6 weeks), and Day 85 (12 weeks) at the following timepoints: 1 hour, 24 hours, 72 hours, 7 days, and 14 days after study drug administration. This schedule will require additional visits solely for sample collection on Study Days 2, 4, 8, 16, 18, 22, 44, 46, 72, and 74.

Pharmacokinetic samples will also be collected on Days 1, 15, 29, 43, 50, 57, 71, 78, and 85 when visit are otherwise scheduled and extra visits are not needed on these days for collection of these samples. The 1-hour, 24-hour, and 14-day post-dose serum concentration data are required for estimation of the PK AUC. In HIV-1 uninfected subjects PK samples will also be drawn on Days -55, -41, -27, and -13.

Study participants who:

1. miss 2 consecutive visits or
2. have more than one treatment visit out of window or
3. have 3 non-treatment visits over 4 weeks that are out of window

will be discontinued from the study and may be replaced. For this reason, it is important to enroll only participants who in the judgement of the investigator are likely to be compliant with the study visit and sample collection schedule.

A complete physical examination will be conducted at Screening. Targeted physical exams will be conducted at designated visits from Day 1 through Day 85 (12 weeks) for HIV-infected and through Day 99/EOS (14 weeks) for HIV-uninfected healthy volunteers. In addition, HIV-1 uninfected

---

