Targeted physical examinations will be conducted at various visits from Day 1 through Day 85 (12 weeks) for HIV-infected subjects, and through Day 99 for HIV-uninfected healthy volunteers. Weight will be recorded at Screening and again at EOS. Immunogenicity samples will be collected at Day 1/Baseline and again at EOS (Day 85 [12 weeks] for HIV-infected subjects or Day 99 [14 weeks] for HIV-uninfected healthy volunteers). IM Group subjects will be asked to return for the final study assessments indicated for the EOS and Follow-up visits (Day 99 [14 weeks] for HIV-infected and Day 113 [16 weeks] for HIV-uninfected see Table 4). Subjects who are discontinued or who withdraw from the study prematurely are also requested to complete the assessments for these two study visits, unless they are re-enrolled HIV-infected individuals participating in the IM study.

Pharmacokinetic samples will be collected after study drug doses at Day 1/Baseline and Days 15, 57, and 71 at the following timepoints: 48 hours, and 7, 10, and 14 days after study drug administration). This schedule will require additional visits solely for sample collection on Study Days 3, 8, 11, 17, 22, 25, 59, 64, 67, 73, 78, and 81. For IM dosing, the 2- and 14-day post-dose serum concentration data are required for the estimation of PK AUC.

Discontinued HIV-1 infected participants who re-enroll after receiving a loading dose of 2000mg IVI and at least one maintenance dose of 800mg IVI given according to the label prior to Day 1 enrollment will not undergo PK assessments between Baseline and the Day 29 visits since these PK samples will already have been collected during the subject's initial study participation. The PK assessments of the re-enrolled participants will be compared between the IVI from their first enrollment and IM from their second enrollment.

In HIV-1 uninfected subjects PK samples will also be drawn on Days -55, -41, -27, and -13.

Study participants who:

1. miss 2 consecutive visits or
2. have more than one treatment visit out of window or
3. have 3 non-treatment visits over 4 weeks that are out of window

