**Listing 16.2.4.4**  
**Post-Administration Observation**

Group	Subject ID	Visit	Visit Date	Observed After Study Drug	Start Time of Observation (hh:mm)	End Time of Observation (hh:mm)	Comments
IM HIV Infected	XX-XXX	XXX	YYYY-MM-DD	YES/NO	XX:XX	XX:XX	XXXXXXXXXXXXXXXXXX
IM HIV Uninfected	XX-XXX	XXX	YYYY-MM-DD	YES/NO	XX:XX	XX:XX	XXXXXXXXXXXXXXXXXX

Westat (Created on DDMMYYYY)  
S:\TMB302\DA\_IM \SAS\L\_POSTINJECT.SAS

**Listing 16.2.5  
PK Results**

Group	Subject ID	Visit	Visit Date (Study Day)	Period [1]	Scheduled Time point	Time of Collection (hh:mm)	Concentration (ng/mL) [2]	AUC (day*ug/mL) [3]
IM HIV Infected	XX-XXX	XXX	YYYY-MM-DD (xx)	XXX	XXX	XX:XX	XXX	XXX
IM HIV Uninfected	XX-XXX	XXX	YYYY-MM-DD (xx)	XXX	XXX	XX:XX	XXX*	XXX

[1] Period represents the timeframe when the visit took place. NOTE - When labs are assessed pre-dose, the value of PERIOD in the lab listings will be previous to the value of PERIOD in listings for post-dose assessments.

[2] \*Indicates TROUGH value.

[3] AUC calculated for Day 1 to Day 15, Day 15 to 29, Day 57 to Day 71 Day 71 to Day 85 (IM Groups).

Westat (Created on DDMMYYYY)  
S:\TMB302\DA\_IM \SAS\L\_PK.SAS

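### IM Group: no PK sample is taken between dosing and 48 h, so the IM/IVI AUC bridge (a secondary objective) can turn on a 0-48 h rule that the readable SAP text does not state

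*Protocol*

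**What the plan says.** Protocol 6.3 has the IM Group sampled after the infusions on Days 1 and 15 and the injections on Days 57 and 71, "at the following timepoints: 48 hours, and 7, 10, and 14 days after study drug administration". Table 4 adds pre-dose samples but, unlike Tables 1 and 3, has no 1-hour post-dose row. Section 3.6 derives these times from the IM Tmax of 2.13 days and applies them to the infusion as well: "blood will be collected at the same timepoints for both routes". Section 6.3 adds: "For IM dosing, the 2- and 14-day post-dose serum concentration data are required for the estimation of PK AUC". It names no required samples for this group's infusion reference.

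For the same 800 mg, 15-minute infusion, Section 6.2 samples the Core Group "at the following timepoints: 1 hour, 24 hours, 72 hours, 7 days, and 14 days after study drug administration". Sections 6.1 and 6.2 both state: "The 1-hour, 24-hour, and 14-day post-dose serum concentration data are required for estimation of the PK AUC".

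On the analysis, the IM SAP's mock Listing 16.2.5, footnote 3, reads "AUC calculated for Day 1 to Day 15, Day 15 to 29, Day 57 to Day 71" and goes on to Day 71-85, so every AUC starts at dosing. Section 4.5 of that SAP and protocol 9.7 specify non-compartmental analysis with no imputation. The readable text gives no trapezoid type and no time-zero or 0-48 h rule. A graphic of the AUC time points in Section 4.5 is not reproduced in the copy reviewed. Both documents attach a formal bridge criterion to this AUC: a 90% confidence interval for the ratio within 80%-125%.

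**The concern.** Protocol 1.3 says that IV concentrations "generally peaked at the end of the infusion period", whereas IM concentrations peak after 2 to 3 days. The highest infusion concentrations therefore fall in the unsampled window, and the IM profile is still rising through most of it. The two routes lose different shares of their AUC, so using the same sampling times does not make the error drop out of the ratio.

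A non-compartmental AUC from time zero needs some concentration at time zero. Several choices are compatible with the text, and they push the ratio in opposite directions. The error is systematic, so more subjects do not reduce it. At stake is whether the IM AUC bridge is declared when it should not be, or missed when it should be declared.

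**Working it through.** **The plan's own figure.** Protocol 9.8 states that 20 subjects give 80% power and reports a within-subject CV of AUC of 7% (median) and 22%-23% (maximum). I used a paired two one-sided test on ln(AUC), limits ±ln(1.25), 5% per side, true ratio 1.00 (assumed, as none is stated), one AUC per route, CV 23%. Power is 79.5% at n=19 and 82.3% at n=20. The stated 20 is reproduced, for an AUC measured without bias.

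**Inputs for the 0-48 h check.** Half-life 75-79 h and IM Tmax 2.13 days (protocol 1.3); interval τ = 14 days; samples at pre-dose, 2, 7, 10 and 14 days (protocol 6.3). Model: one compartment, linear, steady state, true IM/IVI ratio 1.00, with k = ln 2 / half-life and the IM rate ka solved from ln(ka/k)/(ka−k) = 2.13.

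**Share of AUC in 0-48 h.** For the infusion this is (1−e^(−2k))/(1−e^(−14k)).
- 75 h: k = 0.2218/day, 0.358/0.955 = 37.5%.
- 79 h: k = 0.2106/day, 0.344/0.948 = 36.3%.
- IM, by integration: about 22% at both.

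**Worked case, 75 h, linear trapezoid** (units of the single-dose initial concentration; true AUC = 1/k = 4.508).

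| Day | 0 (pre-dose) | 2 | 7 | 10 | 14 |
|---|---|---|---|---|---|
| IVI | 0.047 | 0.672 | 0.222 | 0.114 | 0.047 |
| IM | 0.063 | 0.663 | 0.296 | 0.154 | 0.063 |

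- IVI, days 2-14: 2.235 + 0.504 + 0.322 = 3.061. True IVI area for days 0-2: 0.375 × 4.508 = 1.69.
- IM, days 0-14: 0.726 + 2.398 + 0.675 + 0.434 = 4.233.
- Pre-dose value at time zero: IVI days 0-2 = 0.047 + 0.672 = 0.719, total 3.780, ratio 4.233/3.780 = 1.12.
- IVI-only back-extrapolation: C0 = 0.672 × (0.672/0.222)^(2/5) = 1.047, days 0-2 = 1.719, total 4.780, ratio 0.89.
- 48 h IVI value carried back: days 0-2 = 2 × 0.672 = 1.344, total 4.405, ratio 0.96.

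**Range over 75-79 h and both trapezoid types (linear; linear-up/log-down), true ratio 1.00.**

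| Rule for 0-48 h | Ratio obtained |
|---|---|
| Pre-dose value at time zero, both routes | 1.11-1.15 |
| IVI-only back-extrapolation | 0.89-0.91 |
| 48 h IVI value carried back, pre-dose kept for IM | 0.96-0.98 |

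Dropping the window and using days 2-14 only gives 1.14-1.15, so that is not a way out.

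**Sensitivity to kinetics (all assumed).** At a 168 h half-life the pre-dose rule gives about 1.05. Under saturable elimination with an infusion trough of 30 µg/mL it gives 1.055-1.071. A distribution phase (half-life 12-24 h, 30-50% of the initial concentration) raises it to 1.15-1.28; the carry-back rule then gives 0.98-1.08.

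**Effect on the bridge.** n=20, two AUCs per route, no subject-by-route variance. SDw = √ln(1+CV²), which is 0.070 at CV 7% and 0.227 at CV 23%. The SD of the difference of two-AUC means is √(2·SDw²/2) = SDw. Probability of passing 80%-125%, by the factor that the rule puts on the ratio:

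| CV, true ratio | 1.00 | 1.05 | 1.11 | 1.15 | 0.96-0.98 | 0.89-0.91 |
|---|---|---|---|---|---|---|
| 7%, 0.75 | 0% | 0.4% | 79% | 99.9% | 0% | 0% |
| 7%, 0.90 | 100% | 100% | 100% | 100% | 99.9-100% | 6-42% |
| 23%, 0.75 | 0.2% | 3% | 19% | 41% | <0.1% | 0% |
| 23%, 1.00 | 99% | 95% | 73% | 48% | 96-98% | 65-79% |

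With an assumed subject-by-route SD of 0.15 added (CV 7%: √(0.070² + 0.15²) = 0.165), a true 0.75 passes 2%, 27% and 62% of the time at factors 1.05, 1.11 and 1.15.

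**The case against.** The schedule has a stated rationale, the IM Tmax. IM AUC is a secondary objective, the protocol regards Ctrough as the better marker of efficacy and gives it its own bridge, and the analysis is described as mainly descriptive. The missing graphic, or the laboratory's own procedures, might hold a rule. The sizes come from a linear model although protocol 1.3 says elimination is saturable. The largest pass rates also assume no subject-by-route variance. All of this stands and limits the point. It does not remove it: a formal bridge claim is attached to this AUC, and a graphic cannot supply samples that were never drawn.

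Three stronger readings are tempting, and the documents do not support them.

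- A reader might infer that the plan breaks its own requirement for 1-hour and 24-hour samples. That requirement is stated for the Sentinel and Core Groups; Section 6.3 sets a different one for IM dosing. The contrast is informative but is not a contradiction.
- A reader might infer that the plan favours IM. The direction depends on the rule: above 1 with the pre-dose value at time zero, below 1 with infusion-only back-extrapolation.
- A reader might infer that no AUC bridge can be declared without new samples, or that one identical rule on both routes is the neutral choice. Carrying back the 48 h infusion value gives 0.96-0.98 from the existing samples. Applying the pre-dose rule to both routes is what gives 1.11-1.15, because only for IM is the pre-dose value close to the concentration just after dosing.

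**Conclusion.** The concern holds for the IM AUC comparison only. Nothing is sampled from dosing to 48 h, each AUC includes that window, and no readable rule says how to fill it. When the truth is 1.00, plausible rules return anything from 0.89 to 1.15 at the documented half-life, which is enough to change an 80%-125% verdict. If kinetics are slower or troughs higher, the pre-dose bias is about 1.05-1.07 and the effect is modest: at CV 7% a true 0.75 passes 0.4% of the time at factor 1.05, against 79% at 1.11, or 27% at 1.11 with a subject-by-route SD of 0.15.

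The figures rest on steady state, a one-compartment model, the quoted half-life and Tmax, and equal CV on both routes, so they are a range and not a prediction. The carry-back rule does well partly because it under-counts both routes by similar amounts, which is why it needs sensitivity analyses beside it. The primary Ctrough comparison and the IV push AUC are not affected. This should be fixed, and it can be fixed in the SAP.

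**What to change.** 1. In Section 4.5 of the IM SAP, before the data are analysed, state the trapezoid type and a route-specific 0-48 h rule. Do not use the pre-dose value as the infusion's time-zero concentration. One workable rule is to carry the 48 h infusion value back to time zero and keep the pre-dose value for IM. Say explicitly that this is part of the AUC definition and is not covered by the no-imputation sentence.
2. Report the ratio and its 90% interval under the two bounding rules (pre-dose value at time zero; infusion-only back-extrapolation) as sensitivity analyses. Declare the AUC bridge only if the 80%-125% conclusion is the same under all of them.
3. Optionally, add a supportive analysis with AUC on both routes from the existing population PK model. That model was built in HIV-infected patients, so its fit in HIV-uninfected subjects must be checked first, and protocol 9.7 and SAP 4.5 must be amended to allow it.

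The cost is a little analysis work and a possibly less favourable AUC conclusion. Step 2 can pass no more often than its least favourable rule: at CV 23% and a true 1.00 that is at most 48-73% (factors 1.15-1.11) instead of 99%. At CV 7% a true 1.00 still passes almost always.

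Adding 1-hour and 24-hour samples for subjects not yet dosed is an option, not a condition. In the model above it gives 0.935-0.951, no closer to 1 than the carry-back rule; its value is that data replace an assumption. The sponsor would weigh it against the twelve sample-only days already scheduled and the rule in Section 6.3 that discontinues subjects for out-of-window visits.
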